4. SELECTION AND ENROLLMENT OF PARTICIPANTS

We will be recruiting study participants at University Hospitals Cleveland Medical Center through cardiology clinics (with particular emphasis on heart failure clinics), endocrinology clinics, and the specialized dyspnea clinic run by [name].

Subjects with a diagnosis of Type 2 Diabetes with heart failure who met the inclusion and exclusion criteria will be eligible for participation. Labs drawn within 3 months of the screening visit may be used to determine eligibility.

4.1 Inclusion Criteria:

To be eligible for entry into this study, candidates must meet the following eligibility criteria at the time of enrollment:

- 1. Age > 18 years old but < 75 years old
- 2. No HF hospitalization within 6 months
- 3. Overweight or Obesity defined as BMI > 25 but < 42

4. History of insulin resistance or T2DM or recent HgbA1c (> 5.8% and < 10.5%) and on oral diabetes agents other than SGLT2i

5. EF calculated based on a recent echo/cath/nuclear study at screening (preenrollment) > 50%

6. Stable HFpEF (HF with preserved ejection fraction) medications use of 3-6 months with no plans to changes or add medications for at least 12 weeks (course of the study)

Every effort will be made to ensure that the study population reflects the race/ethnic composition of the target population (subjects with diabetes mellitus type 2 & heart failure with preserved ejection fraction). All patients screened who fulfill inclusion criteria as listed above will be invited, without bias, to participate in the study.

4.2 Exclusion Criteria

Candidates will be excluded from study entry if any of the following criteria exist at the time of enrollment.

- 1. Acute HFpEF hospitalization within 6 months of enrollment.
- 2. CKD stage 4 or 5 (eGFR < 30 ml/min by CKD-EPI equation).

3. Other known causes of HF including poorly controlled hypertension (SBP > 160 mm Hg) or ischemic cardiomyopathy (etc).

4. Anemia (Hgb < 11.0 mg/dL for women and < 12.0 mg/dL for men) or severe thrombocytopenia (platelets < 50,000 mm3)

5. Anticipated changing of HF medication during anticipated study period.

6. HFREF (LV EF < 50%).

7. Acute coronary syndrome, transient ischemic attack, CVA or critical limb ischemia during the last 6 months or coronary/peripheral revascularization within the last 3 months. Severe life threatening illness or live expectancy < 6 months.

8. Contraindications to MRI (metallic implants, severe claustrophobia) or treadmill exercise (limb amputation, severe osteoarthritis or equivalent functional mechanical limitation).

9. Pregnant or nursing mothers

4.3 Study Recruitment Procedures

We will identify eligible participants through screening of heart failure clinics, endocrinology clinics, and the Dyspnea Clinic run by [name].

	Study Variable	Measure	Time Point of Measurements				
Modality			Screening	Baseline: Prior to intervention	Follow up Week 4	Follow up Week 8	12 weeks: end of SGLT2i or placebo
			Visit #1	Visit #2	Phone call	Phone call	Visit #3
Personal	Demographics Characteristics	Demographic Survey	x				
Characteristics	Medical History	Chart Review History & Physical	x		x	x	
Symptom Burden	Dyspnea	MRC Scale	x	x			X
	Fatigue	Lee Fatigue Scale	x	x			x
Quality of Life	Global functional wellness	Kansas City Cardiomyopathy Questionnaire (KCCQ)	x	x			x
		International Physical Activity Questionnaire (IPAQ)	x				x
Medical Characteristics	Vital Signs	Height, Weight, BMI, Blood pressure, Heart rate	x	x			x
	Lipid profile	Total chol, HDL, LDL, TG, NMR lipoprotein particle count	x				x
	Metabolism Chemistries	Fasting glucose, Fasting insulin, glucagon, HOMA-IR, β-HB, hs-CRP, BNP		×			x
Medical Characteristics	Body Composition	DEXA		x			x
	Blood chemistries	Comprehensive metabolic panel, CBC, HgbA1c	x				x
Exercise MRI	Metabolic cart	VO ₂ Peak, RER, VE/VCO ₂ , Anaerobic		x			x
		Threshold					
	Cardiac MRI	SSFP Cine LV EF, velocity encoded PA pressure, LV DGE,T1 mapping ECM %		x			x
Echocardiogram	Transthoracic echo	LVEF, LVMI, diastology, RVSP,		x			×
	Speckle tracking strain rate imaging	Global longitudinal strain rate (GLS)		x			×

Note on Visit Schedule: Screening may occur on same day as 1st baseline testing visit if successfully passed. Labs drawn within 3 months of screening visit will be reviewed to determine subject eligibility. Fasting blood work for Visit #3 may occur 24 hours prior to other testing

Approximately 10ml or 2 teaspoons per visit will be drawn for clinical labs as well as 20ml or 4 teaspoons at visit 2 and 3 for research monocyte studies.

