1. STUDY OBJECTIVES

Primary Objective

This clinical trial will determine if subjects with heart failure with preserved ejection fraction (HFpEF) and type 2 diabetes mellitus (DM2) receiving sodium-glucose cotransporter 2 (SGLT2) inhibitor therapy (ertugliflozin) alters cardiac metabolism compared to placebo in a single blinded (to subject), randomized, parallel group, active controlled, single center experimental design.

Specific Aims

Aim 1: Determine if 12 weeks of SGLTi therapy improves peak exercise oxygen uptake compared to placebo. We will perform cardiac MRI exercise testing (CPETExMR) [N=52 (26 intervention / 26 control)] pre- & post 12 weeks of therapy to measure cardiopulmonary fitness by metabolic cart gas exchange and left ventricular myocardial mass. The primary endpoint of the study will be peak oxygen uptake (VO2 peak, ml/kg/min) as a measure of cardiopulmonary fitness with change in LV mass (gm/m2) as a pre-specified secondary endpoint. The impact of SGLT2i on VO2 kinetics in HFpEF remains unreported.

Aim 2: Evaluate the short term (12 weeks effect of SGLTi on metabolic flexibility in HFpEF compared to baseline function and control group. We will measure glucose and lipid metabolism response to SGLT2 inhibition. Serum samples of glucose and ketone bodies (β -hydroxybutyrate) will be assessed pre- and post-12 weeks of therapy. Fasting serum ketone bodies will be a pre-specified endpoint. Serial serum samples will allow us to generate metabolomics profiles before and after treatment. This experimental design will provide insight into ketone body production, peripheral glucose flux, and circulating lipoparticles in response to SGLTi therapy.

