4.4 Description of Procedures and Evaluations

Consent Procedure

An informed consent document will be provided to individuals interested in participation. Sufficient time will be given to individuals to read, understand and comprehend the goals of the research study. Key study personnel will then have subjects voice their understanding of the research protocol and provide back a lay summary of their role as a study participant. Key study personnel will then review the consent document with the individual and fully describe the goals of the study, the inclusion / exclusion criteria, the planned monitoring, and the study drug administration. Subjects will be told that ertugliflozin (Steglatro) is an FDA approved medication for diabetes but that its specific effects on the heart in heart failure patients is unknown.

Visit #1: Screening and Randomization

Once the participant has signed the informed consent document, a screening visit will take place to ensure that the individual remains eligible for participation. The participant will undergo the following procedures during the screening visit:

- Demographic Information
- Standard health screen
- Urine Pregnancy Test (if applicable)
- Physical examination
- Review of all current medications with reconciliation placed in study binder
- Review and documentation of all medical history.
- \bullet Laboratory assessment (serum CMP, CBC, lipid panel, HgbA1c, insulin, glucagon, HOMA-IR, β -HB).
- Vital Signs
- Symptom surveys (MRC dyspnea scale, Lee fatigue scale, Kansas City Cardiomyopathy Questionnaire)

Demographic information: Prospective volunteers will be required to provide demographic information including their full name, age, gender, race/ethnicity, home/business telephone number(s), date of birth, and emergency contact information. Volunteers will be requested to show a form of photo-identification; these can be any state or federal government issued identification(s), CWRU or UH identity card, and/or club membership card.

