Transthoracic Echocardiography: Standard echocardiography windows will be acquired with special focus on left ventricular ejection fraction (LV EF), LV size, LV wall mass, diastology (mitral inflow velocities, tissue Doppler velocities), left ventricular global longitudinal strain imaging via Speckle tracking (Q Lab 9.0 Philips package), left atrial size and right ventricular systolic pressure as measured by tricuspid regurgitant velocity. All 52 subjects will undergo echo imaging at baseline and study completion in the Mather Pavilion 1800 echo lab. Echocardiography protocols will be supervised by the primary investigator, [name].

Cardiopulmonary Exercise Cardiac Magnetic Resonance Imaging (CPET-ExMR): The CPET-ExMR exercise protocol, combining metabolic exercise testing assessing exercise oxygen consumption (VO2) performed on an MRI-compatible bicycle ergometer or hydraulic treadmill in combination with a MRI stress test (baseline and peak exercise imaging) will be performed at baseline. All subjects will complete the CPET-ExMR prior to starting study drug. CPET-ExMR testing provides whole body metabolic assessment including peak VO2 oxygen consumption, resting metabolic substrate (measured by resting respiratory exchange ratio [RER]), and ventilatory efficiency (VE/VCO2). Cardiac function will be assessed by MRI sequences to quantitate LV mass, LVEF, diastolic and systolic function, extracellular volume fraction (ECV), and tissue edema using T2 mapping.

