Serum Chemistries & Metabolomics: We will assess peripheral metabolic alterations via measurement of fasting serum glucose, insulin, and ketone bodies (β -hydroxybutyrate). These serum chemistries (BNP, hs-CRP, β -HB). will be measured at baseline and following 12 weeks of SGLT2i or placebo to provide direct assessment of SGLT2imodulated peripheral metabolic pathways. Fasting serum ketone bodies will be a prespecified endpoint.

Additional blood samples will be collected and stored for future possible metabolic assessment. We will collect serum samples for biobanking prior to CPET-ExMR exercise testing, immediately after (30 minutes with 10 min window) peak exercise, and post exercise (60 minutes post peak exercise with 10 min window). Whole blood samples will be collected into a vacutainer containing the anticoagulant potassium EDTA. Blood will be placed on ice immediately after collection and centrifuged at 4°C @ 3,500 × g for 15 min to recover the plasma fraction. Plasma will be flash-frozen in liquid nitrogen within 30 min of collection. Potassium EDTA is used as an anti-coagulant to minimize metabolic artifacts associated with anti-coagulation. Serum sample preparation will be supervised by [name].

Symptom Surveys: Symptom survey including severity of baseline dyspnea (MMRC dyspnea scale), fatigue (Lee fatigue scale), and heart failure quality of life (Kansas City Cardiomyopathy Questionnaire) will be completed by the subject during the visit and reviewed by qualified study personnel. Note, if Visit #1 and Visit #2 occur on the same calendar day, only one set of symptom surveys will be completed for both Visit #1 & #2.

Study Intervention Period: At the completion of the Visit #2 baseline testing. The subject will be provided with a 12-week supply (84 days) of study drug (ertugliflozin 5 mg a day or 1 placebo tablet a day) to be provided by the study funder (Merck) and distributed by the UH research pharmacy via prescription from the study physician. Study drug will be provided in a single 12-week supply and be labeled as "Study Medication, take as directed one tablet a day". The subject will be blinded to which treatment arm of the study they were randomized.

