Visit #3: Follow up Testing: At the end of the study intervention period, but prior to the completion of the study medication package (during week #12), the subject will undergo a repeat of the same battery of clinical testing as during Visit #2. Each test will be conducted with an identical protocol to allow for intra-subject assessment of change. Testing during Visit #3 will include: Transthoracic Echocardiography

Cardiopulmonary Exercise Cardiac Magnetic Resonance Imaging (CPET-ExMR) Dual-energy absorptiometry (DEXA) Serum Chemistries & Metabolomics

Symptom Surveys

Study Completion: At the end of the 12 week intervention period, after the subject has completed screening (visit #1), baseline (visit #2), and end of study (visit #3) testing, a SUBJECT COMPLETION CRF must be completed. During the course of the study, it is possible that subjects will be withdrawn from the study. Factors leading to Subject early termination may include, but are not limited to the following.

Subject Withdrawal - A Subject may voluntarily withdraw from the study at any time without affecting their future medical treatment or benefits. In addition, the Investigator may withdraw a Subject from the study if the enrolled Subject does not meet the inclusion/exclusion criteria,

refuses further testing or follow-up evaluations, or for any other reason as determined by the Investigator. A SUBJECT TERMINATION CRF must be completed.

Subject Lost to Follow-Up – If the Investigator has attempted to contact a Subject at least three times and receives no response, the Subject is considered lost to follow-up. The research staff should document at minimum three attempts to contact the Subject, including a certified letter, prior to terminating a Subject from the trial. A SUBJECT COMPLETION CRF must be completed. Subject Death – The Investigator will notify the UH IRB, the local DSMB, the FDA and the Sponsor within 7 days of knowledge of a subject's death. An ADVERSE EVENT and SUBJECT COMPLETION CRF must be completed, as well as a report from the Investigator explaining the nature of the Subject's death.

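### Lipid and lipoparticle samples are not matched for fasting before and after treatment, and only Visit #3 allows blood to be drawn a day before the exercise test

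*Combined protocol and SAP*

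**What the plan says.** Section 1 sets Aim 2 as the effect on metabolic flexibility "compared to baseline function and control group", and names circulating lipoparticles among the things it will inform. Section 3 makes fasting serum β-HB a secondary endpoint.

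In the section 4.3 schedule, the lipid row (which includes the NMR particle count) is marked at screening and Visit #3 only. The chemistry row, "Fasting glucose, Fasting insulin, glucagon, HOMA-IR, β-HB, hs-CRP, BNP", is marked at Visit #2 and Visit #3 only. The note beneath adds: "Fasting blood work for Visit #3 may occur 24 hours prior to other testing". It gives no matching allowance for Visit #2.

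Section 4.4 differs in part. Its Visit #1 list reads "Laboratory assessment (serum CMP, CBC, lipid panel, HgbA1c, insulin, glucagon, HOMA-IR, β -HB", without mention of fasting. Under Visit #2 it says "We will assess peripheral metabolic alterations via measurement of fasting serum glucose, insulin, and ketone bodies". There it also describes biobank samples before and after exercise, and says the exercise test gives "resting metabolic substrate (measured by resting respiratory exchange ratio [RER" among its outputs. For Visit #3 it states: "Each test will be conducted with an identical protocol to allow for intra-subject assessment of change".

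Neither section gives a fasting duration or says whether subjects are fed or fasted for the exercise test.

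**The concern.** A change from baseline is interpretable only if the two measurements are taken under the same conditions. Feeding state is an obvious condition for lipids, lipoprotein particles and resting substrate use, and Aim 2 relies on change from baseline as well as on the control arm.

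Three features of the schedule leave feeding state unmatched or unclear. The lipid baseline comes from a visit with no fasting instruction, while its follow-up comes from one described as fasting. The blood draw may be separated from the exercise day at one visit and not the other. And the text and the schedule disagree on which analytes are drawn at screening. If feeding state differs between visits, part of an apparent treatment or time effect may be nutritional. If the difference is not recorded, it cannot be adjusted for afterwards.

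**Working it through.** **Step 1. Pre- and post-treatment conditions side by side** (sections 4.3 and 4.4)

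| Measure | Pre-treatment | Fasting stated? | Week 12 | Fasting stated? |
|---|---|---|---|---|
| β-HB (endpoint) | Visit #2 in the schedule; also in the Visit #1 list | Visit #2 yes; Visit #1 no | Visit #3 | Yes |
| Lipid panel, NMR particles | Screening only | No | Visit #3 | Yes, as part of Visit #3 blood work |
| Resting RER | Visit #2 exercise day | No | Visit #3 exercise day; blood may be 24 hours earlier | No |
| Pre-exercise biobank sample | Visit #2 exercise day | No | Visit #3 exercise day; blood may be 24 hours earlier | No |

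β-HB is matched if Visit #2 is used. The lipid row is not matched as written, whether or not anyone uses the 24-hour option. The last two rows are uncontrolled. Screening may share a day with baseline testing; for those subjects the lipid sample may in effect be fasting. The lipid baseline may therefore be a mixture across subjects.

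**Step 2. The plan's own figure.** The point itself rests on no figure. The only one attached to these measures is the β-HB sample size in section 7.2: 18, for a 125% rise with SD 117%. The inputs are 288/246 = 117% and (561 − 246)/246 = 128%, against the 125% used.

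Per-arm n = 2(z for alpha + z for power)² (SD/δ)², two-sided 5% assumed:

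- 90% power: 2 × (1.960 + 1.282)² × (117/125)² = 18.4, so 19. On the absolute scale, with δ = 561 − 246 = 315 and SD 288, it is 17.6, so 18.
- 80% power: 2 × (1.960 + 0.842)² × (117/125)² = 13.8, so 14.

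The 18 is reproduced to within one subject as a per-arm number at 90% power. The text says 80% and the table column says 90%; that is a separate matter.

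**Step 3. What a mismatch does.** Let φ be the shift in measured change caused by a non-fasting baseline, the same in both arms. Let p be the proportion of subjects with such a baseline, and σ the SD of change otherwise.

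- Within-arm mean change = true change + φp. The second term does not shrink with more subjects.
- Between-arm difference = true effect + φ(p in the ertugliflozin arm − p in the placebo arm). Feeding at screening precedes treatment, so the bracket is zero in expectation under randomisation.
- The SD of change is multiplied by √[1 + (φ/σ)² p(1 − p)].

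The documents give neither φ nor p.

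**Step 4. How much noise would matter.** This is a yardstick using the β-HB planning values, because none exist for lipids or RER. With 26 per arm, power = Φ[δ/(SD√(2/26)) − 1.960], and 125/(117 × 0.2774) = 3.852. The inflation factors are assumptions.

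| SD multiplied by | Power |
|---|---|
| 1.0 | 97% |
| 1.1 | 94% |
| 1.25 | 87% |
| 1.5 | 73% |
| 2.0 | 49% |

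Since p(1 − p) is at most 0.25, a factor of 1.25 needs (φ/σ)² of at least (1.25² − 1)/0.25 = 2.25, so φ of at least 1.5σ. A factor of 1.5 needs (1.5² − 1)/0.25 = 5, so φ of at least 2.2σ. Noise from a mixed baseline would have to be large to matter much between arms. The within-arm shift φp has no such protection.

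**The case against.** The strongest reply is that the named endpoint is safe. Section 3 defines it as fasting β-HB, section 4.3 labels Visit #2 as baseline, and both the Visit #2 and Visit #3 draws are described as fasting. A reader might infer from the screening list that β-HB has two competing baselines, or that a fed value will be compared with a fasted one. The documents do not support either: nothing calls the screening value a baseline, and a fasting draw moved by 24 hours is still a fasting draw. This stands in full.

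A reader might also infer that subjects will be fasted for the baseline exercise test and fed for the week-12 test, with a predictable shift in RER. The documents do not say so. Neither test's feeding state is stated, the note moves blood only, and the identical-protocol sentence can be read as covering feeding. This also stands: a mismatch is possible, and its direction and size are unknown. Resting RER is not a primary or secondary endpoint, and the biobank samples are stored for possible later use.

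Third, HOMA-IR is calculated from fasting values, so its place in the screening list may imply a fasted screening draw, which would cure the lipid mismatch. This stands only in part. The implication comes from a list that the schedule contradicts, and no fasting instruction is given.

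Finally, randomisation protects the between-arm contrast. It does for a mismatch common to both arms. The 24-hour option is used after randomisation, so it could bias the contrast if its use differed by arm, but nothing in the documents suggests that it would.

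**Conclusion.** The concern holds for Aim 2 measures other than the β-HB endpoint, in three parts.

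1. Lipids and NMR particles have a pre-treatment sample of unstated feeding state and a fasting follow-up. Within-arm change can mix nutrition with treatment, and the between-arm comparison gains noise. This is the firmest part. It assumes that the lipid sample belongs to the Visit #3 fasting blood work, as the note's wording suggests.
2. The Visit #3-only timing option does not fit the promise of identical testing, and leaves resting RER and the pre-exercise sample open to a different feeding state from Visit #2. These are exploratory measures.
3. Sections 4.3 and 4.4 disagree on whether β-HB, insulin, glucagon and HOMA-IR are drawn at screening, and must be reconciled.

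No size can be attached to any of these from the documents. The power range above shows only how much extra noise a contrast planned like β-HB could absorb; it does not estimate the noise to expect. Peak VO2 as the primary endpoint and the definition of the β-HB endpoint are not called into question by this point.

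**What to change.** - Take the baseline lipid panel and NMR particle sample at the existing Visit #2 fasting draw. Any lipid result needed for screening can stay there without serving as baseline.
- Apply one blood-to-test timing rule to Visits #2 and #3, and do each subject's exercise test under the same feeding condition at both. Whether that is fed or fasted is for the investigators; nothing here prescribes it.
- Record time since last meal at both visits, for the blood draw and for the exercise test.
- Reconcile the Visit #1 laboratory list in section 4.4 with the section 4.3 schedule, so that the Visit #2 fasting sample is the sole β-HB baseline.

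The cost is wording in two sections, one added CRF field and a small loss of scheduling flexibility. The lipid sample uses a draw that already takes place.

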4.4 Description of Procedures and Evaluations

Consent Procedure

An informed consent document will be provided to individuals interested in participation. Sufficient time will be given to individuals to read, understand and comprehend the goals of the research study. Key study personnel will then have subjects voice their understanding of the research protocol and provide back a lay summary of their role as a study participant. Key study personnel will then review the consent document with the individual and fully describe the goals of the study, the inclusion / exclusion criteria, the planned monitoring, and the study drug administration. Subjects will be told that ertugliflozin (Steglatro) is an FDA approved medication for diabetes but that its specific effects on the heart in heart failure patients is unknown.

Visit #1: Screening and Randomization

Once the participant has signed the informed consent document, a screening visit will take place to ensure that the individual remains eligible for participation. The participant will undergo the following procedures during the screening visit:

- Demographic Information
- Standard health screen
- Urine Pregnancy Test (if applicable)
- Physical examination
- Review of all current medications with reconciliation placed in study binder
- Review and documentation of all medical history.
- \bullet Laboratory assessment (serum CMP, CBC, lipid panel, HgbA1c, insulin, glucagon, HOMA-IR, β -HB).
- Vital Signs
- Symptom surveys (MRC dyspnea scale, Lee fatigue scale, Kansas City Cardiomyopathy Questionnaire)

Demographic information: Prospective volunteers will be required to provide demographic information including their full name, age, gender, race/ethnicity, home/business telephone number(s), date of birth, and emergency contact information. Volunteers will be requested to show a form of photo-identification; these can be any state or federal government issued identification(s), CWRU or UH identity card, and/or club membership card.

Physical Screening/Evaluation: Volunteer physical screening will include overall assessment of appearance, age, height, weight, body temperature, blood pressure, and pulse. Physical examination will include assessment of at least 10 organ systems with documentation in the study binder. All volunteer screenings are conducted in a private exam room at the medical facility with only the volunteer, the historian, and any other required health care professionals. Volunteers not meeting the pre-stated standards will be excluded from the study.

- 1. The volunteer must appear to be in good health.
- 2. The volunteer must be > 18 years old.
- 3. The volunteer's temperature must be \leq 37.5°C.

4. The volunteer's resting pulse must be between 50 to 100 beats per minutes and free from any pathologic irregularities. Pulses lower than 50 may be acceptable if the volunteer participates in endurance training; the study physician will be consulted for evaluation.

5. Systolic blood pressure must be in the range of 100-160 mm Hg at screening.

6. The volunteer should have a pre-enrollment hemoglobin of > 11.5 mg/dL for women and > 12.5 mg/dL for men).

7. A positive pregnancy test is grounds for subsequent exclusion from the study.

Medical History: The criteria for participation will also include responses to a series of questions designed to protect the volunteer's health and well-being. The interviewer must allow opportunity and encourage the prospective volunteer to ask questions. Any information impacting volunteer eligibility determination should be meticulously documented on the volunteer history questionnaire in sufficient detail to determine the reason for volunteer eligibility or ineligibility.

The questions include the following:

1. Past Medical History Review (PMHx): The volunteer must be in good health on the day of screening. A thorough past medical history will be taken from study volunteers at the time of screening. Particular attention will be paid to heart failure with preserved ejection fraction and diabetes mellitus history. All major hospitalizations in the prior 6 months will be reviewed carefully and likely lead to study exclusion. (Self-limited medical conditions such as acute appendicitis treated with surgical removal would be an exception and will be adjudicated by Study Physician on case-by-case basis.)

2. Current Medication Review: Current medications and duration of treatment will be documented in the study binder. The volunteer be afebrile and symptom free. If a volunteer is taking a medication that causes uncertainty concerning that volunteer's eligibility, blood collection will be deferred.

3. Social and Family History Review: Volunteers will be screened for social behaviors (tobacco, alcohol or drug abuse) and for familial medical conditions.

4. Allergy Review: Study Physician will review all drug allergies with volunteer and document reactions.

5. Review of systems: A full 14 point review of systems will be asked during initial study visit.

Symptom Surveys: Symptom survey including severity of baseline dyspnea (MRC dyspnea scale), fatigue (Lee fatigue scale), and heart failure quality of life (Kansas City Cardiomyopathy Questionnaire) will be completed by the subject during the visit and reviewed by qualified study personnel.

Group assignment protocol: Randomization into treatment group will occur at baseline at a 1:1 ratio. Each subject will assigned an unique identification number for use for the duration of study. Oversight of the master list of identification numbers will be the responsibility of the PI ([name]) and the study coordinator. Randomization will be conducted by an unblinded study personnel (statistician), through REDCap with a "treatment A" and "treatment B" identification using a random number generator. Our statistician will communicate directly with the investigational pharmacy to indicate treatment plan.

Follow up phone calls during 12 week intervention period

Subjects will be contacted by a research staff member at week 4 and week 8 during the intervention period. Phone calls will measure a patient's medication compliance while giving the patients the

opportunity to update the research coordinator on any medical or medication changes made during the study.

Visit #2: Baseline Testing

Subjects that complete Visit #1 screening criteria will be approved by the study physician to be scheduled for Visit #2 baseline testing. Prior to starting therapeutic intervention 12 week period, subjects will undergo a battery of clinical testing including quantification of exercise capacity (CPET) with concurrent cardiovascular magnetic resonance imaging (CPET-Ex-MRI protocol), transthoracic echocardiogram (TTE), and DEXA scanning for body composition analysis.

Transthoracic Echocardiography: Standard echocardiography windows will be acquired with special focus on left ventricular ejection fraction (LV EF), LV size, LV wall mass, diastology (mitral inflow velocities, tissue Doppler velocities), left ventricular global longitudinal strain imaging via Speckle tracking (Q Lab 9.0 Philips package), left atrial size and right ventricular systolic pressure as measured by tricuspid regurgitant velocity. All 52 subjects will undergo echo imaging at baseline and study completion in the Mather Pavilion 1800 echo lab. Echocardiography protocols will be supervised by the primary investigator, [name].

Cardiopulmonary Exercise Cardiac Magnetic Resonance Imaging (CPET-ExMR): The CPET-ExMR exercise protocol, combining metabolic exercise testing assessing exercise oxygen consumption (VO2) performed on an MRI-compatible bicycle ergometer or hydraulic treadmill in combination with a MRI stress test (baseline and peak exercise imaging) will be performed at baseline. All subjects will complete the CPET-ExMR prior to starting study drug. CPET-ExMR testing provides whole body metabolic assessment including peak VO2 oxygen consumption, resting metabolic substrate (measured by resting respiratory exchange ratio [RER]), and ventilatory efficiency (VE/VCO2). Cardiac function will be assessed by MRI sequences to quantitate LV mass, LVEF, diastolic and systolic function, extracellular volume fraction (ECV), and tissue edema using T2 mapping.

The ExMR protocol is performed on a 1.5T scanner (Siemens Avanto) with a 32- channel phased array coil. CMR subjects positioned on the gantry using individualized molds created from deflatable cushions that allow return to the same scanner position post-exercise. Resting cine images consist of 5 short axis and 4 long axis slices performed as non-triggered real-time steady-state free precession acquisitions with temporal generalized auto calibrating partially parallel acquisition (TGRAPPA x4) with the following scan parameters: repetition time (TR) 2.2 ms, echo time (TE) 1.0 ms, flip angle 58°, receiver bandwidth (BW) 1360 Hz/pixel, 40 frames, temporal resolution 51.8 ms, slice thickness 8 mm, average in-plane spatial resolution of 3.9 × 2.6 mm, scan time of 2 s per slice, and an average field of view (FOV) of 281 × 373 mm as previously described by our group.23 After a full exercise protocol is performed, subjects return the MR scanner with identical non-breathholding images acquired along with immediate realtime, through-plane velocity encoding sequence based on gradient-echo echoplanar imaging (GRE-EPI) with Shared Velocity Encoding (SVE) reconstruction. Three orthogonal slices across the pulmonary artery will be prescribed with the highest velocity vector within these slices and the time velocity integral calculated to represent mean PA velocity. T1 mapping will be performed for extracellular volume measurement and delayed gadolinium enhancement (LGE) sequences using Gadolinium DTPA (MagnevistTM, 0.15 mmol/kg) contrast with imaging delay of 5-10 minutes and using inversion time nulling of the myocardium for fibrosis measurement. Cardiopulmonary metabolic cart measurements will be supervised by primary investigator, [name] and cardiac MRI protocols will be supervised in collaboration with coinvestigator [name]. This study will take place in the cardiac MRI scanner at UH Cleveland Medical Center.

Dual-energy absorptiometry (DEXA): Dual-energy absorptiometry (DEXA) scanning will be performed in the Dahms Clinical Research Unit to measure body composition to quantify lean body mass, fat mass, and

Serum Chemistries & Metabolomics: We will assess peripheral metabolic alterations via measurement of fasting serum glucose, insulin, and ketone bodies (β -hydroxybutyrate). These serum chemistries (BNP, hs-CRP, β -HB). will be measured at baseline and following 12 weeks of SGLT2i or placebo to provide direct assessment of SGLT2imodulated peripheral metabolic pathways. Fasting serum ketone bodies will be a prespecified endpoint.

Additional blood samples will be collected and stored for future possible metabolic assessment. We will collect serum samples for biobanking prior to CPET-ExMR exercise testing, immediately after (30 minutes with 10 min window) peak exercise, and post exercise (60 minutes post peak exercise with 10 min window). Whole blood samples will be collected into a vacutainer containing the anticoagulant potassium EDTA. Blood will be placed on ice immediately after collection and centrifuged at 4°C @ 3,500 × g for 15 min to recover the plasma fraction. Plasma will be flash-frozen in liquid nitrogen within 30 min of collection. Potassium EDTA is used as an anti-coagulant to minimize metabolic artifacts associated with anti-coagulation. Serum sample preparation will be supervised by [name].

Symptom Surveys: Symptom survey including severity of baseline dyspnea (MMRC dyspnea scale), fatigue (Lee fatigue scale), and heart failure quality of life (Kansas City Cardiomyopathy Questionnaire) will be completed by the subject during the visit and reviewed by qualified study personnel. Note, if Visit #1 and Visit #2 occur on the same calendar day, only one set of symptom surveys will be completed for both Visit #1 & #2.

Study Intervention Period: At the completion of the Visit #2 baseline testing. The subject will be provided with a 12-week supply (84 days) of study drug (ertugliflozin 5 mg a day or 1 placebo tablet a day) to be provided by the study funder (Merck) and distributed by the UH research pharmacy via prescription from the study physician. Study drug will be provided in a single 12-week supply and be labeled as "Study Medication, take as directed one tablet a day". The subject will be blinded to which treatment arm of the study they were randomized.

Visit #3: Follow up Testing: At the end of the study intervention period, but prior to the completion of the study medication package (during week #12), the subject will undergo a repeat of the same battery of clinical testing as during Visit #2. Each test will be conducted with an identical protocol to allow for intra-subject assessment of change. Testing during Visit #3 will include: Transthoracic Echocardiography

Cardiopulmonary Exercise Cardiac Magnetic Resonance Imaging (CPET-ExMR) Dual-energy absorptiometry (DEXA) Serum Chemistries & Metabolomics

Symptom Surveys

Study Completion: At the end of the 12 week intervention period, after the subject has completed screening (visit #1), baseline (visit #2), and end of study (visit #3) testing, a SUBJECT COMPLETION CRF must be completed. During the course of the study, it is possible that subjects will be withdrawn from the study. Factors leading to Subject early termination may include, but are not limited to the following.

Subject Withdrawal - A Subject may voluntarily withdraw from the study at any time without affecting their future medical treatment or benefits. In addition, the Investigator may withdraw a Subject from the study if the enrolled Subject does not meet the inclusion/exclusion criteria,

refuses further testing or follow-up evaluations, or for any other reason as determined by the Investigator. A SUBJECT TERMINATION CRF must be completed.

Subject Lost to Follow-Up – If the Investigator has attempted to contact a Subject at least three times and receives no response, the Subject is considered lost to follow-up. The research staff should document at minimum three attempts to contact the Subject, including a certified letter, prior to terminating a Subject from the trial. A SUBJECT COMPLETION CRF must be completed. Subject Death – The Investigator will notify the UH IRB, the local DSMB, the FDA and the Sponsor within 7 days of knowledge of a subject's death. An ADVERSE EVENT and SUBJECT COMPLETION CRF must be completed, as well as a report from the Investigator explaining the nature of the Subject's death.

